5.0 STUDY OBJECTIVES AND ENDPOINTS

5.1 Objectives

5.1.1 Primary Objective

To assess the relative bioavailability and bioequivalence of 2 strengths of the fixed-dose combination tablet product SYR-322-4833 BL compared to the individual alogliptin and pioglitazone tablets in healthy Russian subjects.

5.1.2 Additional Objective

To perform a comparative analysis of AE data after the administration of SYR-322-4833 BL and after coadministration of alogliptin and pioglitazone to healthy volunteers within the scope of the trial.

5.2 Endpoints

5.2.1 Primary Endpoints

The following plasma pharmacokinetic (PK) parameters of alogliptin and pioglitazone will be derived on Day 1 of each period:

- Maximum observed concentration (C_{max}).
- Area under the concentration-time curve from the time 0 to time 72 hours (AUC_{72}).

5.2.2 Additional Endpoints

5.2.2.1 Exploratory

CCI

5.2.2.2 Criteria of Subject Condition Assessment

- Percentage of subjects who experience at least 1 postdose AE.
- Percentage of subjects who have clinically significant changes in laboratory tests at least once postdose.
- Percentage of subjects who have clinically significant changes in vital sign measurements at least once postdose.
- Percentage of subjects who have clinically significant changes in electrocardiogram (ECG) parameters at least once postdose.
- Percentage of subjects who experience at least 1 postdose event of hypoglycemia.

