13. The subject has current or recent (within 6 months) gastrointestinal disease that would be expected to influence the absorption of drugs (ie, a history of malabsorption, esophageal reflux, peptic ulcer disease, erosive esophagitis, frequent [more than once per week] occurrence of heartburn, or any surgical intervention).
14. The subject has a non-standard diet (eg, vegetarian or vegan) or lifestyle (including nighttime work, extreme physical activity such as weights lifting), which may interfere with the trial.
15. The subject has a history of cancer, except basal cell carcinoma which has been in remission for at least 5 years prior to Day 1 of Period 1.
16. The subject has a positive test result for hepatitis B surface antigen (HBsAg), hepatitis C virus (HCV) antibody, human immunodeficiency virus (HIV) antibody or syphilis at Screening.
17. The subject has used nicotine-containing products (including but not limited to cigarettes, pipes, cigars, chewing tobacco, nicotine patch or nicotine gum) within 28 days prior to Check-in Day -1. Cotinine test is positive at Screening or Check-in (Day -1).
18. The subject has poor peripheral venous access.

19. The subject has donated or lost 450 mL or more of his or her blood volume (including plasmapheresis), or had a transfusion of any blood product within 30 days prior to Day 1 of Period 1.
20. The subject has abnormalities in routine physician examination, laboratory and/or ECG findings.
21. The subject has a systolic blood pressure >130 mm Hg or <100 mm Hg, diastolic blood pressure >90 mm Hg or <70 mm Hg; heart rate <60 beats per minute (bpm) or >80 bpm at Screening (Day -28 to Day -2) or Check-in to Period 1 (Day -1).
22. The subject has consumed caffeine or xanthine-containing food or drinks within 72 hours prior to Check-in (Day -1).
23. The subject has dehydration due to vomiting, diarrhea, or any other reason within 24 hours prior to study start.
24. The subject has drug intolerance.

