13.1.4 Subject Condition Assessments

Subject condition assessments will be performed using the Safety Set. All subject condition assessments, including AEs, clinical laboratory evaluations, 12-lead ECG results, and vital signs will be summarized with descriptive statistics, where appropriate, and presented in the data listings.

All AEs will be coded using MedDRA and presented in the data listings.

A postdose AE is defined as an AE that occurs after the subject receives the first dose of study medication and within 30 days after the last dose of study medication is received. Summary of AEs will include numbers and percentages of subjects experiencing AEs by system organ class and preferred term. AEs will also be summarized based on their intensity and relationship to study medication by system organ class and preferred term. If a subject has more than 1 AE that codes to the same preferred term, the subject will be counted only once for that preferred term within regimen. Similarly, if a subject has more than 1 AE within a system organ class category, the subject will be counted only once in the system organ class category within the regimen. In the intensity summary, a subject will be counted only in the highest intensity category for each preferred term and each organ class. In the relationship to study medication summary, a subject will be counted only in the highest relationship category for each preferred term and each system organ class. Each summary table will include incidences of adverse events for each regimen and overall.

All AE summary tables will be listed in the SAP.

AEs will be summarized using preferred term and primary system organ class.

Individual results for clinical hematology and serum chemistry laboratory tests that are outside of normal range and results that meet Takeda predefined criteria for markedly abnormal values will be considered as clinically significant and identified in summary tables, if applicable. Observed values and change from Baseline will be summarized by regimen. All laboratory values will be presented in the data listings.

Individual vital sign values that meet the Takeda predefined markedly abnormal criteria will be considered as clinically significant and identified in a summary table. The vital sign measurements at predefined time points and change from Baseline will be summarized by regimen. All vital signs data will be presented in the data listing.

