7.11.3 Vital Signs

Refer to [Appendix A](#) for scheduled vital signs measurement visits. Individual results for vital sign measurements that meet the Takeda predefined vital signs MAV criteria in [Appendix C](#) will be presented in a data listing. All vital sign data will be presented in the listings. Vital sign MAVs will be flagged in the listings.

7.11.4 12-Lead ECGs

The scheduled 12-lead ECG data will be collected according to [Appendix A](#), including baseline and the final visit. The ECG evaluations will be categorized as Normal; Abnormal, not clinically significant; and Abnormal, clinically significant. ECG results will be presented as a shift from baseline table and all ECG data will be presented in data listings.

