Appendix C Criteria for Abnormal Changes from Baseline of Vital Signs

| Parameter | Unit | Lower Criteria | Upper Criteria |
|--------------------------|-------------|-----------------------|-----------------------|
| Pulse | bpm | <50 | >120 |
| Systolic blood pressure | mm Hg | <85 | >180 |
| Diastolic blood pressure | mm Hg | <50 | >110 |
| Body temperature | °C | < 35.6 | >37.7 |

ELECTRONIC SIGNATURES

| Signed by | Meaning of Signature | Server Date (dd-MMM-yyyy HH:mm 'UTC') |
|-----------|--------------------------------|--|
| PPD | Statistical Approval | 20-Jun-2018 14:26 UTC |
| | Pharmacovigilance Approval | 20-Jun-2018 14:28 UTC |
| | Biostatistics Approval | 20-Jun-2018 14:40 UTC |
| | Clinical Pharmacology Approval | 27-Jun-2018 21:27 UTC |
| | Clinical Science Approval | 03-Jul-2018 19:48 UTC |

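### The vital-sign endpoint is worded as changes but scored by absolute limits with no reference to the predose value, and the SAP drops the protocol's change-from-baseline summary

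*Protocol*

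**What the plan says.** Protocol 5.2.2.2 lists as an endpoint "Percentage of subjects who have clinically significant changes in vital sign measurements at least once postdose", and SAP 5.2 repeats it.

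Protocol 13.1.4 gives the scoring rule: "Individual vital sign values that meet the Takeda predefined markedly abnormal criteria will be considered as clinically significant and identified in a summary table". Next to it, as a separate descriptive display, it says: "The vital sign measurements at predefined time points and change from Baseline will be summarized by regimen".

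The criteria are in SAP Appendix C, titled "Criteria for Abnormal Changes from Baseline of Vital Signs". Every cell is an absolute limit: pulse <50 or >120 bpm, systolic <85 or >180 mm Hg, diastolic <50 or >110 mm Hg, temperature <35.6 or >37.7 °C.

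SAP 7.11.3 says that "Individual results for vital sign measurements that meet the Takeda predefined vital signs MAV criteria in" Appendix C will be listed. It also lists and flags all vital-sign data, but plans no table and no change from baseline. SAP 7.13 records no changes.

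Entry is limited by Protocol 7.2, exclusion 21: "The subject has a systolic blood pressure >130 mm Hg or <100 mm Hg, diastolic blood pressure >90 mm Hg or <70 mm Hg", with heart rate outside 60 to 80 bpm also excluded. These limits apply at Screening and at check-in to Period 1. There is no numeric limit for temperature. Protocol 10.1.1 excludes subjects with vital-sign abnormalities before the first dose but gives no threshold. Appendix A, footnote (e), in both documents, has vital signs measured just before dosing on Day 1 of all four periods.

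**The concern.** The endpoint name and the Appendix C title both promise a comparison with baseline, and the rule makes none. Two consequences follow.

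First, a reading that was beyond a limit before dosing and stayed there is reported as a clinically significant change under whichever regimen was given in that period.

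Second, the size of a change does not decide whether it counts; the level reached does. A large rise from a low starting value can go uncounted while a smaller fall to a low level counts.

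The percentage is part of the tolerability comparison between the fixed-dose combination and the separate tablets. If it is reported under its present name, readers will take it as a statement about change after dosing. The display that would show changes directly is promised in the protocol and missing from the SAP.

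**Working it through.** The documents state no figure to reproduce here. The check compares the Appendix C limits with the exclusion 21 limits, then looks at how the rule behaves under an illustrative model.

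**Step 1. Changes that cannot count from a baseline inside the entry limits.** Heart rate in exclusion 21 is taken as pulse in Appendix C. The criteria are strict inequalities, so a value equal to a limit does not count.

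- Rise that never counts = upper criterion minus upper entry limit.
- Fall that never counts = lower entry limit minus lower criterion.

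| Parameter | Entry limits | Appendix C | Rise never counted | Fall never counted |
|---|---|---|---|---|
| Systolic (mm Hg) | 100–130 | <85, >180 | 180 − 130 = 50 | 100 − 85 = 15 |
| Diastolic (mm Hg) | 70–90 | <50, >110 | 110 − 90 = 20 | 70 − 50 = 20 |
| Pulse (bpm) | 60–80 | <50, >120 | 120 − 80 = 40 | 60 − 50 = 10 |

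From the bottom of the entry range the uncounted rise is larger: 180 − 100 = 80 mm Hg systolic and 120 − 60 = 60 bpm. As an example of the ordering, systolic 100 to 84 (−16) counts, but 128 to 86 (−42) and 130 to 180 (+50) do not.

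**Step 2. Baselines outside the entry limits.** SAP 7.1.1 takes baseline before the first dose on Day 1 of Period 1, after the last check of exclusion 21. If, as an assumption, the Day 1 systolic value is 135 to 145, the uncounted rise shrinks to 180 − 135 = 45 down to 180 − 145 = 35 mm Hg. For a pulse of 85 to 95 it shrinks to 35 down to 25 bpm.

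**Step 3. Unchanged values.** An unchanged systolic, diastolic or pulse value inside the entry limits can never meet Appendix C. An unchanged temperature of 35.5 or 37.8 °C does meet it, with zero change.

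**Step 4. Response of the rule under an illustrative model.** The assumptions are not from the documents. Baselines are normal, truncated to the entry limits, with mean/SD of systolic 118/10, diastolic 76/7 and pulse 70/8. The change is normal with SD 10. There were 2,000,000 draws, and one postdose reading was compared with Appendix C.

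| Mean shift | Systolic flagged | Diastolic flagged | Pulse flagged |
|---|---|---|---|
| −30 | 45% | 57% | 81% |
| −20 | 18% | 24% | 50% |
| +20 | 0.01% | 14% | 0.4% |
| +30 | 0.3% | 43% | 3.8% |

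With no shift, 0.5% are flagged on systolic and 3.8% on pulse, essentially all low readings. A mean pulse rise of 30 bpm thus gives the same percentage as no effect. With SD of change 8 to 12, a +30 shift is flagged in 0.05% to 0.8% (systolic) and 1.8% to 6.3% (pulse).

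**Step 5. Protocol against SAP.** Protocol 13.1.4 commits to a by-regimen summary of values and change from baseline, and to a summary table of markedly abnormal values. SAP 7.11.3 contains listings and flags only. For laboratory tests, SAP 7.11.2 does specify change from baseline and the number and percentage meeting the criteria, so the omission is specific to vital signs.

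**The case against.** Protocol 13.1.4 defines clinical significance by the level reached, and it uses abnormal-value criteria for laboratory tests and ECGs too. That is a legitimate choice. For systolic, diastolic and pulse readings that start inside the entry limits, any flagged value is necessarily a change. This stands, and it is why absolute limits need not be replaced.

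Three stronger readings are tempting, and the documents do not support them.

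- A reader might infer that the endpoint could hardly give anything but a near-zero result. Step 4 contradicts this: the rule responds to falls in all three parameters and to diastolic rises. The insensitivity is confined to systolic and pulse rises. The protocol's background (4.1.2) lists reduced blood pressure among pioglitazone's effects, and the risks named in 4.3 include neither hypertension nor tachycardia.
- A reader might infer that baseline is used nowhere. Protocol 13.1.4 does plan a change-from-baseline summary. The accurate statement is that the scoring rule ignores baseline and that SAP 7.11.3 does not carry the summary through. The opening of SAP 7.11 says safety data are summarized by study arm, but it names no vital-sign statistic.
- A reader might infer that rises of 50 mm Hg or 40 bpm can never count for anyone. That holds only for baselines inside limits checked at Screening and at Day -1 of Period 1.

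The temperature example also has a limit. Under Protocol 10.1.1, a reading judged abnormal before the first dose excludes the subject. An unchanged 35.5 °C counts only if it was not judged abnormal then, or if it is first seen before dosing in Periods 2 to 4.

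Finally, the stakes are low. The endpoint is descriptive, no decision rule uses it, and an unfavourable sign can still be recorded as an adverse event.

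**Conclusion.** The mismatch is real and minor. The endpoint and the Appendix C title speak of changes, while the rule scores levels without regard to the predose value. A pre-existing, unchanged abnormal reading is counted as a change. From baselines inside the entry limits, systolic rises up to 50 mm Hg and pulse rises up to 40 bpm are not counted. Those two figures are exact arithmetic given in-range baselines. The flag rates rest on the assumed baselines and SD of change, and serve only to show which directions the rule can see. The documents give no basis for estimating how many subjects would be miscounted. Separately, two vital-sign summaries promised in Protocol 13.1.4 are absent from SAP 7.11.3, so the SAP as written tabulates neither the endpoint percentage nor the changes. The primary comparisons on Cmax and AUC72 are untouched.

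**What to change.** 1. In SAP 7.11.3 and Appendix C, count an Appendix C value toward the endpoint only if the predose Day 1 value of the same period did not meet the same criterion. That value is already collected under Appendix A, footnote (e). State which readings count as postdose for each period, including whether check-in and predose readings of the next period belong to the preceding regimen. Otherwise an abnormality that first appears there would be lost.
2. Restore to SAP 7.11.3 the by-regimen change-from-baseline summary and the table of markedly abnormal values from Protocol 13.1.4, or record the departure in SAP 7.13.
3. Reconcile the Appendix C title and the endpoint wording with the absolute limits the table contains.

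The cost is SAP wording, a few programming lines and slightly fewer counted events. No new measurements are needed.

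Adding change thresholds is for the sponsor to decide and is not required. It is a trade-off: with an illustrative 20-unit threshold and SD of change 10, chance flags for systolic pressure rise from about 0.5% to 4.5% per comparison. Over four independent comparisons that is 1 − 0.955⁴ ≈ 17% of subjects.

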6.0 STUDY DESIGN AND DESCRIPTION

6.1 Study Design

This is a single-center, open-label, randomized, 4-sequence, 4-period, single dose crossover study involving 72 healthy adult, male and female subjects between the ages of 18 and 55 years, inclusive.

Subjects will be randomized in the order in which they are enrolled into the study. The 72 eligible subjects will be randomized to 1 of 4 drug intake sequences in a 1:1:1:1 ratio. Due to the large sample size, volunteers may be divided into 2 or 3 cohorts according to space limitations at the site. All cohorts will be dosed sequentially.

The study consists of a Screening Period (Days -28 to Day-2) and 4 Drug Intake Periods. A washout interval of 7 days (beginning immediately after dosing on Day 1) will separate the doses of each study period. Subjects will be admitted into the clinic on Day -1 (Day 7 of the preceding period for Periods 2, 3, and 4) and will be dosed on Day 1 of each period. Starting on Day 1 of each period, blood samples for determination of alogliptin and pioglitazone plasma concentrations will be collected predose through 72 hours postdose. The subjects will be discharged from the clinic after the 24-hour blood sample collection on Day 2 of each period and will return to the clinic for the 36-hour blood sample collection on Day 2 and on Days 3 and 4 of each period to complete study procedures. Final Visit procedures will be performed on Day 4 of Period 4 and a Follow-up call will be made 14 days \pm 2 days following the last dose of study drug.

A schematic of the study design is included as [Figure 6.a](#). A schedule of assessments is listed in [Appendix A](#).

Figure 6.a Schematic of Study Design

Predose Period			Drug Intake Period (c)								
Screening (a)	Check-in (b)		Period 1		Period 2		Period 3		Period 4		
Days -28 to -2	Day -1		Day 1 Dosing	Days 2 to at least 7	Day 1 Dosing	Days 2 to at least 7	Day 1 Dosing	Days 2 to at least 7	Day 1 (d) Dosing	Days 2 to 3	Day 4 Final Visit/ET
		Sequence I (n=18)	A	WO	B	WO	C	WO	D	WO	
		Sequence II (n=18)	B		C		D		A		
		Sequence III (n=18)	C		D		A		B		
		Sequence IV (n=18)	D		A		B		C		

A=SYR-322-4833 BL (25 mg + 15 mg) (test regimen), B=alogliptin 25 mg + pioglitazone 15 mg (reference regimen), C=SYR-322-4833 BL (25 mg + 30 mg) (test regimen), D=alogliptin 25 mg + pioglitazone 30 mg (reference regimen), ET=Early Termination, WO=Washout of 7 days between dosing.

(a) Screening may consist of 1 or more visits. Subjects will sign an informed consent form at the first visit and return to the clinic in a fasted state for safety laboratory testing at the second visit.

(b) Subjects are admitted into the clinic on Day -1 of each period (~Day 7 of the preceding period for Periods 2, 3, and 4).

(c) Randomization occurs on Day 1 of Period 1. Subjects check out of the unit on Day 2 following the 24-hour blood sample collection but return to the clinic for the 36-hour blood sample collection on Day 2 and on Days 3 and 4 of each period to complete study procedures.

(d) Follow-up call will be made 14 days ±2 days following the last dose of study drug.

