8.3 Randomization Code Creation and Storage

The randomization schedule will be generated prior to the start of the study, and will be provided to the site pharmacist prior to the start of this study. All randomization information will be stored in a secured area, accessible only by authorized personnel.

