9.3.3 Drug Intake/Washout Period

Subjects will be confined to the clinic from Check-in (Day -1) of Dosing Period 1 until the 24-hour blood sample has been collected on Day 2 of Dosing Period 1 and from Day 7 of Dosing Periods 1,

2, and 3 until the 24-hour blood sample has been collected on Day 2 of Dosing Periods 2, 3, and 4, respectively. Subjects will be discharged or released from the unit unless deemed inappropriate by the investigator because of safety concerns. Subjects will return to the clinic for the 36-hour blood sample collection on Day 2 and on Days 3 and 4 of each period to complete study procedures.

There is a 7-day washout interval between the dose in each period.

The study consists of a Screening Period (Days -28 to Day-2) and 4 Drug Intake Periods. A washout interval of 7 days (beginning immediately after dosing on Day 1 of Period 1) will separate the doses of each study period. Subjects will be admitted into the clinic on Day -1 (at least 10 hours prior to study drug administration), will be dosed on Day 1 and discharged from the clinic after the 24-hour blood sample has been collected on Day 2 of each period. Blood samples for determination of alogliptin and pioglitazone plasma concentrations will be collected prior to dosing on Day 1 through 72 hours postdose.

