13.0 STATISTICAL METHODS

13.1 Statistical and Analytical Plans

A statistical analysis plan (SAP) will be prepared and finalized prior to database lock. This document will provide further details regarding the definition of analysis variables and analysis methodology to address all study objectives.

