13.1.3 PK Analysis

Descriptive statistics (eg, N, mean, SD, median, minimum, and maximum) will be used to summarize the plasma concentrations of alogliptin and pioglitazone by regimen and scheduled sampling time point. Individual plasma concentration data for alogliptin and pioglitazone will be presented in the data listings.

Descriptive statistics (N, mean, SD, SE, percent coefficient of variation [%CV], median, minimum, and maximum) will be used to summarize the PK parameters of alogliptin and pioglitazone for each regimen. Geometric means will be computed for AUCs and C_{max} .

Statistical inference to determine if the FDC tablet is bioequivalent to alogliptin and pioglitazone administered as individual tablets will be performed using an analysis of variance (ANOVA) model with effects for regimen, period, sequence, and subjects nested within sequence. The effect due to subject nested within sequence will be considered a random effect in the ANOVA model while all other effects will be treated as fixed. The ANOVA model will be applied to the natural logarithms of AUC_{72} and C_{max} of alogliptin or pioglitazone as dependent variables to compare the test and reference regimens.

Within the framework of ANOVA model for natural logarithms of AUC_{72} and C_{max} , the ratios and the 90% confidence intervals (CIs) for the ratios of central values of the test regimen relative to the

reference regimen will be provided. The ratios will be obtained as the antilog of the difference of the LS means on a natural logarithm scale, and the 90% CIs will be obtained by taking the antilog of the 90% CI for the difference between the LS means on the natural logarithmic scale.

Bioequivalence between administration of alogliptin and pioglitazone as an FDC tablet and as individual tablets will be concluded if the 90% CIs are within the range of (0.80, 1.25) for C_{max} and AUC_{72} .

Alternative statistical analyses will be used if deemed appropriate.

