4.4 Study Design

This is a single-center, open-label, randomized, 4-sequence, 4-period, single dose crossover study involving 72 healthy adult, male and female subjects between the ages of 18 and 55 years, inclusive.

Subjects will be randomized in the order in which they are enrolled into the study. The 72 eligible subjects will be randomized to 1 of 4 drug intake sequences in a 1:1:1:1 ratio. Due to the large sample size, volunteers may be divided into 2 or 3 cohorts according to space limitations at the site. All cohorts will be dosed sequentially.

The study consists of a Screening Period (Days -28 to Day-2) and 4 Drug Intake Periods. A washout interval of 7 days (beginning immediately after dosing on Day 1) will separate the doses of each study period. Subjects will be admitted into the clinic on Day -1 (Day 7 of the preceding period for Periods 2, 3, and 4) and will be dosed on Day 1 of each period. Starting on Day 1 of each period, blood samples for determination of alogliptin and pioglitazone plasma concentrations will be collected predose through 72 hours postdose. The subjects will be discharged from the clinic after the 24-hour blood sample collection on Day 2 of each period and will return to the clinic for the 36-hour blood sample collection on Day 2 and on Days 3 and 4 of each period to complete study procedures. Final Visit procedures will be performed on Day 4 of Period 4 and a Follow-up call will be made 14 days \pm 2 days following the last dose of study drug.

A schematic of the study design is included as [Figure 1](#). A schedule of assessments is listed in [Appendix A](#).

Figure 1 Schematic of Study Design

| Predose Period | | | Drug Intake Period (c) | | | | | | | |
|----------------|--------------|---------------------|------------------------|----------------------|--------------|----------------------|--------------|----------------------|------------------|-------------|
| Screening (a) | Check-in (b) | | Period 1 | | Period 2 | | Period 3 | | Period 4 | |
| Days -28 to -2 | Day -1 | | Day 1 Dosing | Days 2 to at least 7 | Day 1 Dosing | Days 2 to at least 7 | Day 1 Dosing | Days 2 to at least 7 | Day 1 (d) Dosing | Days 2 to 3 |
| | | Sequence I (n=18) | A | WO | B | WO | C | WO | D | WO |
| | | Sequence II (n=18) | B | | C | | D | | A | |
| | | Sequence III (n=18) | C | | D | | A | | B | |
| | | Sequence IV (n=18) | D | | A | | B | | C | |

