For each analyte, an analysis of variance (ANOVA) will be performed on natural logarithm transformed C_{max} and AUC_{72} with factors for sequence, the subject nested within sequence, period and regimen. The random effect subject nested within sequence will be the error term for testing the sequence effect. Other factors will be tested with the residual as the error term. For the relative bioavailability (BA) determination, pairwise comparisons will be performed to assess the relative BA of alogliptin and pioglitazone via point estimates and 90% confidence interval (CI) for the ratio of C_{max} and AUC_{72} central values for Regimen A (test) versus Regimen B (reference) as well as Regimen C (test) versus Regimen D (reference). CCI [REDACTED]

A conclusion of bioequivalence in the PK of each analyte between test regimen will be reached if the 90% CIs for C_{max} and AUC_{72} are within the (0.80-1.25) interval.

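### If the optional sequential cohorts are used, the primary ANOVA should fit period within cohort; one common period effect can widen the 90% CIs

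*Protocol*

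**What the plan says.** Protocol 6.1 and SAP 4.4 allow the 72 subjects to be split into groups: "Due to the large sample size, volunteers may be divided into 2 or 3 cohorts according to space limitations at the site". The protocol adds: "All cohorts will be dosed sequentially". So Period 1 of one cohort falls on different dates from Period 1 of the next.

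Protocol 13.1.3 and the Study Summary specify an ANOVA "model with effects for regimen, period, sequence, and subjects nested within sequence". SAP 7.9.1 gives the same model, "with factors for sequence, the subject nested within sequence, period and regimen", and tests regimen against the residual. No visible text has a cohort term, a period effect within cohort, or a statement that sequences are balanced within cohort. On allocation, Protocol 8.3 says "The randomization schedule will be generated prior to the start of the study", and Protocol 6.1 gives a 1:1:1:1 ratio overall.

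Protocol 13.3 and SAP 6.0 claim more than 80% power for pioglitazone Cmax at both strengths, assuming CV 33%, a ratio between 0.95 and 1.05 and 14% drop-out.

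**The concern.** With one common period term, the first periods of all cohorts share one fitted value although they happen at different times. A constant difference between cohorts does no harm, because each subject belongs to one cohort and the subject effect takes it up. A cohort-specific period effect is not modelled. It inflates the residual mean square and so widens every test-versus-reference interval.

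At stake is some power to show bioequivalence. False-positive risk does not rise: the error runs towards failing to show bioequivalence.

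**Working it through.** **Inputs.** From Protocol 13.3: 72 enrolled, 14% drop-out (72 × 0.86 = 62 completers), CV 33%, ratio 0.95. From Protocol 13.1.3: 90% CI within 0.80 to 1.25. From Protocol 6.1: the four-sequence square of Figure 6.a and 2 or 3 cohorts. Assumed, because no document gives it: cohort-by-period effects drawn from N(0, SD²) on the log scale, with SD from 0 to 0.30.

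**The plan's own figure.**
- Within-subject log SD = √ln(1 + 0.33²) = 0.3215.
- Residual df = 3 × 62 − 6 = 180.
- CI half-width = t(0.95, 180) × 0.3215 × √(2/62) = 0.0955.
- Power from two one-sided tests at ratio 0.95 is 90.6% per strength, and 0.906² = 82.0% for both if the two contrasts are independent. The stated figure above 80% reproduces.

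**Effect on the planned residual.** With k cohorts, the expected residual mean square rises by (k − 1) × 3 × (62/k) × SD² / 180. For k = 3 and SD 0.20 this is 2 × 3 × 20.67 × 0.04 / 180 = 0.0276, against 0.3215² = 0.1034. The half-width grows by √(1.267) = 1.125, to about 0.107.

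**Simulation.** There were 10,000 trials per setting, with 62 of 72 subjects kept at random. The same data were fitted with common period and with period within cohort. Not balanced means 18 per sequence overall, but sequences falling at random across cohorts. Power is per comparison, averaged over A–B and C–D (Monte Carlo error about 0.003 to 0.004).

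| Cohorts, sequences | Planned CI width relative to period within cohort, SD 0 / 0.05 / 0.10 / 0.20 / 0.30 | Planned power | Power, period within cohort |
|---|---|---|---|
| 3, balanced | −0.3 / +0.6 / +3.0 / +12.1 / +25.5% | 0.907 / 0.898 / 0.889 / 0.853 / 0.788 | 0.899–0.906 |
| 3, not balanced | −1.7 / −0.9 / +1.5 / +10.3 / +23.4% | 0.905 / 0.902 / 0.890 / 0.837 / 0.745 | 0.895 |
| 2, balanced | −0.1 / +0.5 / +2.3 / +9.2 / +19.5% | 0.907 / 0.902 / 0.897 / 0.870 / 0.822 | 0.903–0.906 |
| 2, not balanced | −0.8 / −0.3 / +1.5 / +8.1 / +18.0% | 0.906 / 0.907 / 0.896 / 0.852 / 0.788 | 0.902–0.904 |

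Planned power per comparison drops below 80% at an SD of about 0.24 (3 cohorts, not balanced), 0.28 (2, not balanced) and between 0.28 and 0.30 (3, balanced). With 2 balanced cohorts it is still 0.822 at 0.30.

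**Both strengths together**, planned model, 4,000 trials per setting, SD 0.10 / 0.15 / 0.20:
- 2 cohorts, balanced: 0.806 / 0.779 / 0.760
- 3 cohorts, balanced: 0.812 / 0.785 / 0.733
- 2 cohorts, not balanced: 0.796 / 0.775 / 0.727
- 3 cohorts, not balanced: 0.799 / 0.751 / 0.691

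Period within cohort keeps joint power at about 0.80 to 0.83.

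**Type I error** at a true ratio of 1.25, SD 0 to 0.30: planned 0.024 to 0.051; period within cohort 0.047 to 0.051.

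**If the 33% CV already contains this variance** (3 balanced cohorts, SD 0.05 / 0.10 / 0.20), planned power per comparison is 0.911 / 0.914 / 0.933, so nothing is lost against the target. The planned CI is still 0.6 / 3.2 / 15.9% wider than it need be.

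**The case against.** The planned model is valid, unbiased on average, and errs against the sponsor, so this could be called a preference between two sound models. It matters only if cohorts are used and their period effects differ appreciably. Conduct favours small differences: one site, dosing within an hour of 08:00, meals meant to be identical across periods, and validated assays. Cohorts may also be close in time. Subjects are "discharged from the clinic after the 24-hour blood sample has been collected on Day 2 of each period", a stay of about two nights, so three cohorts could start about 2 days apart within one 7-day cycle. They could equally follow one another three weeks or more apart. An SD of 0.20 is large: the same period in two cohorts would then differ with SD 0.20 × √2 = 0.28, about 1.3-fold. At 0.05 to 0.10 the loss per comparison is close to simulation error.

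All of that stands and keeps the point minor. So does a second argument. Without balance, period within cohort narrows the CI only above an SD of about 0.075 (3 cohorts) or 0.06 (2 cohorts), and below that it costs a little precision. That cost is at most 1.7% in width, and balance within cohort removes most of it.

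The gap may also be closed where we cannot see. SAP 7.9.1 has redacted text right after the pairwise comparisons, the randomization schedule is not shown, and PK-parameter details are deferred to a Clinical Pharmacology Analysis Plan that is not supplied. The protocol's allowance for alternative analyses does not close it, because it names no model and would leave the choice until the data exist, in an open-label study.

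**Conclusion.** The concern holds as a low-cost improvement, not as an error that threatens the conclusion. If 2 or 3 cohorts are dosed, the visible model leaves cohort-specific period effects in the residual. The loss per comparison is 0 to 1 power point at an assumed SD of 0.05 to 0.10 and about 3 to 6 points at 0.20. If the power claim in Protocol 13.3 means both strengths together, the margin is thin: about 82% with no cohort effect, passing below 80% at an SD of about 0.10 to 0.15.

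The size depends entirely on the assumed SD and on that variance being additional to the 33% CV. One qualification to the statement that only precision is affected: without balance within cohort, a single realized allocation can shift the estimate, but the shift averages to zero and coverage stays near 90%. Fitting period within cohort removes it. A regimen effect that differs between cohorts is a separate question, not addressed here.

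**What to change.** Unless the redacted text already does so, add to SAP 7.9.1:

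> If more than one cohort is dosed, period is fitted within cohort and subject (random) is nested in sequence and cohort; regimen, the 90% CIs and the 0.80–1.25 rule are unchanged. If one cohort is dosed, the model above applies.

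Separate cohort and sequence-by-cohort terms are not needed. With between-subject variance assumed equal to within-subject variance, they change the A–B standard error by 0% with complete subjects and by at most 0.02% when 10 of 72 subjects miss 1 to 3 periods.

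Ask the holder of the randomization schedule to confirm balance of sequences within cohort, without printing the block size in this open-label protocol. Balance is feasible: 36/4 = 9 per sequence with two cohorts, 24/4 = 6 with three.

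**Cost.** Residual df fall from 180 to 177 or 174. If cohorts do not differ, the CI is 0.1% (2 cohorts) to 0.3% (3 cohorts) wider with balance and 0.8% to 1.7% wider without; in the worst of these, power is 0.895 instead of 0.905. The revised SAP needs its functional approvals again before database lock. Protocol 13.1 says of the SAP: "This document will provide further details regarding the definition of analysis variables and analysis methodology to address all study objectives". On that footing no protocol amendment is needed for this alone, but Protocol 13.1.3 and the Study Summary name the model and should be aligned at the next amendment.
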